9.3 Procedures at each visit

First Phase

9.3.1 Screening/First Visit

Screening visit, Day 0: The potential participants will be given the Patient Information and Informed Consent form. The trial will be explained including how many visits are expected as well as the type of testing that they will complete. They are given time during the appointment to decide whether to participate in the study. If they choose not to take part in the study they will not sign the consent form, and the appointment will finish. If they choose to join the trial they will sign and date the consent form. No trial activities will be performed before the consent form is signed and dated by the subject and the investigator. Subjects will receive a copy of the signed consent form. A hearing history is then taken, and otoscopy is performed. A hearing test is performed, and inclusion/exclusion criteria will be determined. The RMD is programmed to a first fit and adjusted using REM data to match the gain targets. They are given an IFU about the RMD and the product questionnaire to complete at home regarding the RMD. They are scheduled for the second visit. Any AEs are reported in the CRFs.

9.3.2 Fitting/Second Visit

Fitting Visit, Day 10 +/- 5: Otoscopy is performed, and the subjects are fitted with the IMD. Output of the IMD is measured, and the fitting adjusted using REM to better match the gain targets. They are randomised regarding the hearing aid order and blinded for the live feedback test which is performed with the RMD and the IMD. The subjects return the RMD. The subjects return the completed product questionnaire from the first visit and are given the same questionnaire to complete at home regarding the IMD. They are given an IFU about the IMD. They are scheduled for the third visit. Any AEs are reported in the CRFs.

9.3.3 Final/Third Visit

Final Visit, Day 20 +/- 5: Otoscopy is performed. They are randomised regarding the test condition order and the word lists and blinded for the speech testing. Speech tests are made with the WaKo in three conditions: unaided, aided with the RMD, and aided with the IMD. The subjects return the IMD. The subjects return the completed product questionnaire from the second visit and complete a standardized questionnaire (SSQ) and a preference questionnaire during the appointment. They are notified that the testing has finished. They will return to wearing their own hearing aids. They are reminded to make appointments at the clinic for any fine-tuning or maintenance of their own hearing aids. Any AEs are reported in the CRFs.

Second Phase

9.3.4 Screening/First Visit

Screening Visit, Day 50 +/- 15: The potential participants will be given the Patient Information and Informed Consent form. The trial will be explained including how many visits are expected as well as the type of testing that they will complete. They are given time during the appointment to decide whether to participate in the study. If they choose not to take part in the study they will not sign the consent form, and the appointment will finish. If they choose to join the trial they will sign and date the consent form. No trial activities will be performed before the consent form is signed and dated by the subject and the investigator. Subjects will receive a copy of the signed consent form. A hearing history is then taken, and otoscopy is performed. A hearing test is performed, and inclusion/exclusion criteria will be determined. For subjects that choose to participate in phase one and phase two, a new consent form is not required, and the screening will not be completed again. The RMD is programmed to a first fit and adjusted using REM data to match the gain targets. They are given an IFU about the RMD and a product questionnaire to complete at home regarding the RMD. They are scheduled for the second visit. Any AEs are reported in the CRFs.

9.3.5 Fitting/Second Visit

Fitting Visit, Day 60 +/- 5: Otoscopy is performed, and the subjects are fitted with the IMD. Output of the IMD is measured, and the fitting adjusted using REM to better match the gain targets. They are randomised regarding the hearing aid order and blinded for the live feedback test which is performed with the RMD and the IMD. The subjects return the RMD. The subjects return the completed product

questionnaire from the first visit and are given the same questionnaire to complete at home regarding the IMD. They are given an IFU about the IMD. They are scheduled for the third visit. Any AEs are reported in the CRFs.

9.3.6 Final/Third Visit

Final Visit, Day 70 +/- 5: Otoscopy is performed. They are randomised regarding the test condition order and the word lists and blinded for the speech testing. Speech tests are made with the WaKo in three conditions: unaided, aided with the RMD, and aided with the IMD. The subjects return the IMD. The subjects return the completed product questionnaire from the second visit and complete a standardized questionnaire (SSQ) and a preference questionnaire during the appointment. They are notified that the testing has finished. They will return to wearing their own hearing aids. They are reminded to make appointments at the clinic for any fine-tuning or maintenance of their own hearing aids. Any AEs are reported in the CRFs.

Third Phase

9.3.7 Screening/First Visit

Screening visit, Day 0: The potential participants will be given the Patient Information and Informed Consent form. The trial will be explained including how many visits are expected as well as the type of testing that they will complete. They are given time during the appointment to decide whether to participate in the study. If they choose not to take part in the study they will not sign the consent form, and the appointment will finish. If they choose to join the trial they will sign and date the consent form. No trial activities will be performed before the consent form is signed and dated by the subject and the investigator. Subjects will receive a copy of the signed consent form. A hearing history is then taken, and otoscopy is performed. A hearing test is performed, and inclusion/exclusion criteria will be determined. The RMD is programmed to a first fit and adjusted using REM data to match the gain targets. They are given an IFU about the RMD and a product questionnaire to complete at home regarding the RMD. They are scheduled for the second visit. Any AEs are reported in the CRFs.

9.3.8 Fitting/Second Visit

Fitting Visit, Day 10 +/- 5: Otoscopy is performed, and the subjects are fitted with the IMD. Output of the IMD is measured, and the fitting adjusted using REM to better match the gain targets. They are randomised regarding the hearing aid order and blinded for the live feedback test which is performed with the RMD and the IMD. The subjects return the RMD. The subjects return the completed product questionnaire from the first visit and are given the same questionnaire to complete at home regarding the IMD. They are given an IFU about the IMD. They are scheduled for the third visit. Any AEs are reported in the CRFs.

9.3.9 Final/Third Visit

Preference Visit, Day 20 +/- 5: Otoscopy is performed. They are randomised regarding the test condition order and the word lists and blinded for the speech testing. Speech tests are made with the WaKo in three conditions: unaided, aided with the RMD, and aided with the IMD. The subjects return the IMD. The subjects return the completed product questionnaire from the second visit and complete a standardized questionnaire (SSQ) and a preference questionnaire during the appointment. They are notified that the testing has finished. They will return to wearing their own hearing aids. They are reminded to make appointments at the clinic for any fine-tuning or maintenance of their own hearing aids. Any AEs are reported in the CRFs.

10. SAFETY

The Sponsor's SOPs provide more detail on safety reporting.

10.1 Medical Device Category C studies

Device deficiencies and all **adverse events (AE)** including all **serious adverse events (SAE)** are collected, fully investigated and documented in the source document and appropriate case report form (CRF) during the entire study period, i.e. from patient's informed consent until the last protocol-specific procedure, including a safety follow-up period [ISO 14155]. Documentation includes dates of event, treatment, resolution, assessment of seriousness and causal relationship to device and/or study procedure.

The information on AEs is systematically collected by the clinician at each study visit. They will follow the procedures outlined in SOP ID106_AE Reporting. The subjects are asked at each appointment if they have experienced any events since the last appointment. During the appointments the subjects are then asked questions about the event to gather details and to determine the severity of the event. If a subject reports pain that results in the inability to use the device, he will be withdrawn from the study in order to avoid any pain from using the device and to remove partial data from the study. For reports of pain caused by insertion or the dome itself, the problem can be addressed in the clinic. For example, a different style or size of dome can be placed on the hearing aid, and re-training of insertion can be performed with the subject to avoid wrong or forceful insertion of the device. For reported pain they will be advised to not wear the device for 24 hours before resuming use.

Foreseeable adverse events outlined in the risk management file include discomfort caused by the domes, domes or filters falling off in the ear, no amplification coming from the device causing alarms or traffic to not be heard by the subject, skin reaction if chemical profile of device is changed, maximum output of the device exceeding 132 dB SPL, battery exploding or catching fire, swallowing of a lithium battery, and the device affecting other medical devices worn by the subject. The incidence of all of these risks or adverse events is improbable. To mitigate the risk, the IFU describes how to insert the device, how to change the domes, and how to change a battery in case of no amplification. The IFU describes how to clean the device, domes, and filters in order to not introduce cleaning agents that might change the chemical profile of the hardware of the device. The labelling warns of the potential maximum output of the device. The IFU instructs the user to keep the device away from explosive environments, and to keep them away from children or pets that might swallow the batteries. The IFU warns of interference with implantable devices.

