7.4 Criteria for withdrawal / discontinuation of participants

Participants are allowed to withdraw from the study at any time and for any reason. They do not have to share the reasons with the investigator. They will be asked to return the IMD. If the decision to withdraw is made by the investigator, the PI will inform the subject in person that they are no longer needed for the study. Reasons for withdrawing a participant from the study could be for non-compliance during testing, unreliable responses, medical reasons such as an ear infection, or the study may need

to be stopped or postponed. Any data gathered from these subjects will be used for the current study. All data will remain encoded because results are only recorded using the identification code of the subject. There are normally at least five “back-up” test participants on the list to replace those that withdraw or are withdrawn. The “back-up” participants have already been screened and deemed to be appropriate for the study.

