8.5 Data Collection and Follow-up for withdrawn participants

Any data that is collected will be kept in the data management database. The data will remain encoded because results are only recorded using the identification code of the subject. The analysis and report will include a summarized section based on the data available from all recruited subjects and another section based on the data from the subjects that complete the entire protocol will be analysed. Withdrawn subjects will have the same follow-up as those subjects that complete the trial. As all subjects are taken from the Bernafon database, all participants, including those that withdraw, are welcome to return to the clinic for fine-tuning and maintenance as needed.

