9.2 Assessments of outcomes

9.2.1 Assessment of primary outcome

The primary outcome is the live feedback testing results of the IMD compared with the RMD. The hearing aids will be programmed with the same gain and feedback elicited in simulated real-life situations that cause feedback including: Inserting and removing the hearing aids from the ears, holding a telephone up to the ear, sitting close to a wall, putting the hand up to the ear. The subjects will answer questions about the annoyance caused by the elicited feedback. The feedback test will be tested with the RMD and the IMD at the second appointment.

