11.4 Planned Analyses

11.4.1 Datasets to be analysed, analysis populations

Primary analysis of the primary outcome will be based on the intention-to-treat (ITT). The ITT population will include all participants with associated primary outcome data, excluding only subjects who were deemed ineligible following the screening visit, those who withdrew from the trial and were unwilling for their previously collected data to be utilised or those who failed to provide baseline.

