11.5 Handling of missing data and drop-outs

Unless specified otherwise in each objective, no statistical techniques will be used to impute missing data. If a subject's data are missing for any reason, that subject will not be included in that portion of the analysis. The number of subjects included in each analysis will be reported so that the potential impact of missing data can be assessed.

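### Section 10.1 gives removal of partial data as a purpose of withdrawing participants for pain, against sections 7.4 and 8.5 and the ITT definition in 11.4.1

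*Protocol*

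**What the plan says.** Section 10.1 of the protocol, on safety, states that a participant whose pain makes the device unusable is withdrawn, "in order to avoid any pain from using the device and to remove partial data from the study". It does not say what partial data are or from which dataset they would be removed.

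The sections that deal with data handling read differently:

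- **7.4** covers withdrawal by the participant and by the investigator, and lists medical reasons among the latter: "Any data gathered from these subjects will be used for the current study".
- **8.3** says that the data of a participant who asks to stop using the investigational device (IMD) remain in the results.
- **8.5** keeps all collected data in the database and plans two parts of the report: "The analysis and report will include a summarized section based on the data available from all recruited subjects", and a separate section on those who complete the protocol.
- **11.4.1** defines the primary analysis set: "The ITT population will include all participants with associated primary outcome data, excluding only subjects who were deemed ineligible following the screening visit". The only other exclusions are participants who withdrew and refuse use of their data, and those without baseline.
- **11.5** allows no imputation unless an objective specifies otherwise. A participant with missing data stays out only where the data are missing: "that subject will not be included in that portion of the analysis".

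On timing, 9.2.1 says "The feedback test will be tested with the RMD and the IMD at the second appointment". Section 9.3.2 describes participants as "blinded for the live feedback test which is performed with the RMD and the IMD" at that visit, and 9.3.5 and 9.3.8 repeat this for Phases 2 and 3. The IMD field period starts after it.

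**The concern.** Removing data is written as an aim of the withdrawal, on a par with avoiding pain. That is a statement about data handling placed in the safety section, and it runs against every section that sets data rules.

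The trigger is an event that may be caused by the device under test, and it can occur after the primary outcome has been measured. If site staff or the analyst acted on 10.1, participants could leave the analysis after testing for a reason related to the device, while the protocol describes the primary analysis as intention-to-treat. The investigator also holds the order list for the lab tests (6.2.1, 6.3) and the field period is unblinded (6.2.2), so a loosely worded ground for removing data should not stand.

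The product questionnaire is exposed too. It carries the safety questions on unexpected device behaviour (5.3, 9.2.3), and a participant who stops because of pain is likely to have an incomplete set of questionnaires.

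**Working it through.** The contradiction is textual, so the check is to follow a participant withdrawn for pain through each rule. Section 10.1 says only that the device cannot be used and does not limit this to the IMD, so there are two cases.

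**Case A: pain in the IMD field period, after Visit 2**

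| Rule | What happens to the data |
|---|---|
| 9.2.1, 9.3.2 | Live feedback test already done with both devices: complete primary pair |
| 11.4.1 | In the ITT set; withdrawal for pain is not an exclusion |
| 11.5 | Missing Visit 3 data (speech, SSQ, preference) affect only those analyses; the Visit 2 pair stays |
| 7.4 | Data gathered are used |
| 8.3 | Same principle, written for participants who ask to stop using the IMD |
| 8.5 | Data kept; participant counted in the all-recruited section, not in the completer section |
| 10.1 | Partial data removed from the study |

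Only the last row points to removal.

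**Case B: pain in the reference-device field period, before Visit 2**

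There is no primary pair, so the participant is outside the ITT set in any event and 11.4.1 is not breached. Sections 7.4 and 8.5 still require other collected data to be used and kept, and 10.1 still contradicts them.

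**Possible meanings of partial data**

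1. *Everything from a participant who did not finish.* In Case A this removes a complete primary pair and conflicts with 7.4, 8.5 and 11.4.1.
2. *Only incomplete field or questionnaire data.* The primary pair is safe, but 7.4 is still contradicted, and the affected data include the questionnaire with the safety questions.
3. *Only absence from the completer section of 8.5.* This fits 8.5, but the clause speaks of removal from the study. A non-completer is outside the completer section without any removal.

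The document does not say which is meant.

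**Scale**

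Planned participants per phase (11.2): 22, 22 and 11. These figures reproduce with a one-sided paired t-test at 2.5%: effect size 0.94 with 11 participants gives 80.2% power (stated: 80%), and 0.65 with 22 gives 82.8% (stated: 83%). The sample size is not in dispute.

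Share of planned pairs lost for each primary pair removed:

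- Phase 3: 1/11 = 9.1%
- Phase 1 or Phase 2: 1/22 = 4.5%

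The protocol gives no expected number of pain withdrawals, so no total is computed.

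**The case against.** The strongest reply is that the clause is a motive in a safety paragraph and not a data rule. It names no dataset, deletion step or exclusion from analysis. The sections that do set rules agree with each other, and 12.1.2 adds that a signed CRF is required even for those who do not finish. On this view 11.4.1 and 11.5 already specify the primary analysis correctly. A primary pair completed at Visit 2 is also not naturally called partial.

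Much of this stands. Sections 11.4.1 and 11.5 do govern the primary set, and the broad reading is not the only one. The number affected is also likely to be small: of the foreseeable events listed in 10.1, which include dome discomfort, the protocol says "The incidence of all of these risks or adverse events is improbable". Pain from insertion or the dome can be addressed in the clinic, and 7.4 provides screened replacements. The primary comparison is within participant, so removing someone takes out both device scores together, and no direction of bias follows.

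It does not dispose of the point. The narrow reading still contradicts 7.4, and the completer reading does not explain removal from the study. Replacements can restore the count but not the data of the participant removed. Section 10.1 is also where staff will look when pain is reported, and what they find there is a contrary aim.

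**Conclusion.** The concern holds: section 10.1 is wrong as written. Its conflict with 7.4 and 8.5 does not depend on when the withdrawal happens. Its conflict with the ITT definition in 11.4.1 arises if partial data is read to include a primary pair already obtained, which requires withdrawal after Visit 2.

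The likely impact is modest. Each pair removed would be 9.1% of the planned pairs in Phase 3 and 4.5% in Phase 1 or 2, and few such withdrawals are expected. No loss of power is claimed, and the direction and size of any bias cannot be derived from the protocol. It should be corrected because it supplies a written ground for dropping data after a device-related event.

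**What to change.** In 10.1, delete the part of the sentence that makes removing partial data a purpose of the withdrawal. Add one sentence there: data collected up to withdrawal are handled under 11.4.1, 11.5 and 8.5. References to 7.4 and 8.3 could be added for completeness. If the clause was meant only to keep such participants out of the completer section, say that in 8.5 instead.

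The cost is one deleted clause and one added sentence. Visits, tests, sample size and analysis method do not change, and the clinical rule on when to withdraw a participant is left as it is.

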10.1.1 Definition and Assessment of (Serious) Adverse Events and other safety related events

Adverse Event (AE)

Any untoward medical occurrence, unintended disease or injury or any untoward clinical signs (including an abnormal laboratory finding) in participants, users or other persons whether or not related to the investigational medical device [ISO 14155: 3.2].

This includes events related to the IMD or the RMD and to the procedures involved. For users or other persons this is restricted to events related to the investigational medical device.

Adverse Device Effect (ADE)

Adverse event related to the use of an investigational medical device [ISO 14155: 3.1].

This includes any adverse event resulting from insufficient or inadequate instructions for use, deployment, implantation, installation, operation, or any malfunction of the investigational medical device. This includes any event that is a result of a use error or intentional misuse.

AEs/ADEs include:

- Exacerbation of a pre-existing disease or condition.
- Increase in the frequency or intensity of a pre-existing episodic disease or medical condition.
- Any disease or medical condition detected or diagnosed after treatment with the study intervention device even though it may have been present yet undetected prior to the start of the clinical investigation.
- Any continuous persistent disease or symptoms present at baseline that worsen following the start of the clinical investigation.

- Events considered by the investigator to be related to any of the clinical investigation-mandated procedures.
- Abnormal assessments, e.g. physical examination findings, will be reported as AEs/ADEs if they represent a clinically significant finding that was not present at baseline or that has significantly worsened during the course of the clinical investigation.
- Test abnormalities will be reported as AEs/ADEs if they represent a clinically significant finding, symptomatic or not, which was not present at baseline or has significantly worsened during the course of the clinical investigation.

AEs/ADEs do not include:

- Pre-planned interventions or occurrences of endpoints specified in the CIP are not considered AEs/ADEs, if not defined otherwise.
- Unrelated medical or surgical procedures, e.g. surgery, endoscopy, tooth extraction, transfusion. However, the event leading to the procedure may be considered an AE. If this event is serious, the procedure will be described in the SAE/SADE narrative.
- Any pre-existing disease or medical condition that remains stable and does not worsen during the course of study participation.
- Situations in which an adverse change did not occur, e.g., hospitalizations for unrelated cosmetic elective surgery or for social and/or convenience reasons.

Serious Adverse Event (SAE) [European regulation on medical devices 2017/745, art. 58].

Any adverse event that led to any of the following:

- (a) death,
- (b) serious deterioration in the health of the subject that resulted in any of the following:
 - (i) life-threatening illness or injury,
 - (ii) permanent impairment of a body structure or a body function,
 - (iii) hospitalisation or prolongation of patient hospitalisation,
 - (iv) medical or surgical intervention to prevent life-threatening illness or injury or permanent impairment to a body structure or a body function,
 - (v) chronic disease,
- (c) foetal distress, foetal death or a congenital physical or mental impairment or birth defect.

This includes device deficiencies that might have led to a serious adverse event if a) suitable action had not been taken or b) intervention had not been made or c) if circumstances had been less fortunate. These are handled under the SAE reporting system. A planned hospitalisation for pre-existing condition, or a procedure required by the protocol, without a serious deterioration in health, is not considered to be a serious adverse event.

Device deficiency

Inadequacy of a medical device related to its identity, quality, durability, reliability, safety or performance, such as malfunction, misuse or use error and inadequate labelling [ISO 14155: 3.15].

Health hazards that require measures

Findings in the trial that may affect the safety of study participants and, which require preventive or corrective measures intended to protect the health and safety of study participants SAE [ClinO Art. 37].

Causal Relationship of SAE [MEDDEV 2.7/3 revision 3, May 2015].

A causal relationship towards the medical device or study procedure should be rated as follows:

- **Not related:** The relationship to the device or procedures can be excluded.
- **Unlikely:** The relationship with the use of the device seems not relevant and/or the event can be reasonably explained by another cause, but additional information may be obtained.

- **Possible:** The relationship with the use of the investigational device is weak but cannot be ruled out completely. Alternative causes are also possible.
- **Probable:** The relationship with the use of the investigational device seems relevant and/or the event cannot reasonably be explained by another cause.
- **Causal relationship:** The serious event is associated with the investigational device or with procedures beyond reasonable doubt.

Device deficiencies that might have led to an SAE are always related to the medical device.

